#### 6.2. Efficacy Endpoints

• Neuropathy Impairment Score (NIS)

The NIS will be evaluated at baseline (i.e., before the start of treatment with this drug), at Weeks 78 and 156, and at the end/discontinuation of treatment.

The NIS is a measure of neuropathy that involves 37 assessments of the cranial nerves (items 1 to 5), muscle weakness (items 6 to 24), reflexes (items 25 to 29), and sensation (index finger: items 30 to 33, great toe: items 34 to 37); for items assessed bilaterally, the mean of the right and left is used as the score for the item.

The total NIS score, NIS-lower limbs (NIS-LL) score, and NIS-upper limbs (NIS-UL) score will be determined as a measure of the degree of systemic neuropathy, neuropathy of lower limbs, and neuropathy of upper limbs, respectively.

Subscores assessed include the scores for cranial nerves, muscle weakness, reflexes, and sensation, as well as muscle weakness scores for lower limbs and upper limbs, reflexes scores for lower limbs and upper limbs, and sensation scores for great toe and index finger.

	Cranial Nerves	Muscle Weakness	Reflexes score	Sensation score
	score	score		
Total score [0, 244]		Sum of it	ems 1-37	
NIS-LL score [0, 88]		Sum of items 17-24 (Muscle Weakness for lower limbs)	Sum of items 28-29 (Reflexes for lower limbs)	Sum of items 34-37 (Sensation for great toe)
NIS-UL score [0, 156]	Sum of items 1-5	Sum of items 6-16 (Muscle Weakness for upper limbs)	Sum of items 25-27 (Reflexes for upper limbs)	Sum of items 30-33 (Sensation for index finger)

Each item for cranial nerves and muscle weakness will be graded on the following 8-point scale:

0: Normal

1:25% Weak

2: 50% Weak
3: 75% Weak
3.25: Move against gravity
3.5: Movement, gravity eliminated
3.75: Muscle flicker, no movement
4: Paralysis

Each item for reflexes and sensation will be graded on the following 3-point scale:

- 0: Normal
- 1: Decreased
- 2: Absent
- Norfolk Quality of Life Diabetic Neuropathy (QOL-DN)

Quality of life in studied patients will be assessed using Norfolk QOL-DN at baseline, at Weeks 78 and 156, and at the end/discontinuation of treatment.

The QOL-DN questionnaire consists of symptoms part (items 1-7) and activities of daily living part (items 8-35).

The total QOL (TQOL) score as well as subscores for physical function/large nerve fiber disorder, activities of daily living, symptoms, small nerve fiber disorder, and autonomic neuropathy will be determined.

TQOL score [-4, 136]	Sum of all items 1-35	
Physical Function/Large Nerve Fiber Disorder score [-4, 56]	Sum of items 8, 11, 13-15, 24, and 27-35	
Activities of Daily Living score [0, 20]	Sum of items 12, 22, 23, 25, and 26	
Symptoms score [0, 32]	Sum of items 1-7, and 9	
Small Nerve Fiber Disorder score [0, 16]	Sum of items 10, and 16-18	
Autonomic Neuropathy score [0, 12]	Sum of items 19-21	

Items 1-7 will be evaluated by assessing whether the relevant symptom exists in each of the four regions (feet, legs, hands, and arms).

0: None

- 1: Present in one region
- 2: Present in two regions
- 3: Present in three regions

4: Present in all four regions

Items 8-26 will be graded on the following 5-point scale:

- 0: No difficulty
- 1: Minimal difficulty
- 2: Mild difficulty
- 3: Moderate difficulty
- 4: Severe difficulty

Items 27-30 and 33-35 will be graded on the following 5-point scale:

- 0: None at all
- 1: A little
- 2: Some
- 3: Moderately
- 4: Severely

Item 31 will be graded on the following 5-point scale:

- -2: Excellent -1: Very good
- 0: Good
- 1: Ordinary
- 2: Bad

Item 32 will be graded on the following 5-point scale:

- -2: Considerably better
- -1: Better to some extent
- 0: Almost unchanged
- 1: Worse to some extent
- 2: Considerably worse
- Modified Body Mass Index (mBMI)

mBMI will be measured at baseline, at Weeks 26, 52, 78, 104, 130, and 156, and at the end/discontinuation of treatment.

mBMI = (serum albumin  $[g/dL]/10) \times BMI$ 

BMI = body weight  $[kg]/(body height [cm]/100)^2$ 

• Ambulatory Status (walking ability rating scale in the polyneuropathy dysfunction score)

Ambulatory status will be assessed at baseline, at Weeks 78 and 156, and at the end/discontinuation of treatment.

Ambulatory status (walking ability) will be graded on the following 6-point scale:

PFIZER CONFIDENTIAL Page 19 0: Good

1: Able to walk without difficulty despite of sensory disorder in the lower extremities

2: Able to walk without assistance despite of some difficulties

3a: Able to walk with one stick or crutch

3b: Able to walk with two sticks or crutches

4: Unable to walk, restricted to wheelchair or bedridden

• Neurological Assessment

Neurological assessment will be performed at baseline, at Weeks 52 (1 year), 104 (2 years), and 156 (3 years), and at the end/discontinuation of treatment.

The neurological assessments consist of those of motor function, tendon reflexes, light touch, pin prick, vibration, and position sense. Each evaluation item will be evaluated bilaterally except those for the trunk. If a result for the trunk has been recorded for both right and left side, the higher value will be adopted. The total score, motor score, reflexes score, and sensation score will be determined.

Total score	Sum of the motor, reflexes, and		
[0, 294]	sensation scores		
Motor score	Sum of the results for motor function grading		
[0, 160]	Sum of the results for motor function grading		
Reflexes score	Sum of the results for tendon reflexes grading		
[0, 10]	Sum of the results for tendon reflexes grading		
Sensation score	Sum of the results for light touch, pin prick, vibration,		
[0, 124]	and position sense		

Motor function will be graded on the following 6-point scale:

0: No contraction

1: Flicker contraction

2: Muscle contraction with active motion with gravity eliminated

3: Full range of motion against gravity

4: Full range of motion against gravity with some resistance

5: Full range of motion against gravity with maximum resistance for that muscle

For the purpose of determining the motor score, however, grading should be inverted to read 0 as normal and 5 as abnormal.

5: No contraction

4: Flicker contraction

3: Muscle contraction with active motion with gravity eliminated

2: Full range of motion against gravity

1: Full range of motion against gravity with some resistance

0: Full range of motion against gravity with maximum resistance for that muscle

Tendon reflexes will be graded on the following 2-point scale:

- 0: Present
- 1: Absent

Test results for light touch, pin prick, vibration, and position sense will be graded on the following 3-point scale:

- 0: Normal
- 1: Decrease
- 2: Absent
- Evaluation of Survival Time

Survival time will be evaluated by setting death as the event of interest. For patients who complete the study, survival status will be determined on the first follow-up date exceeding 3 years after the start of treatment with this drug at the own site. In the case of death, information on the cause, i.e., whether the death is due to TTR-FAP or to another cause (including unknown) will also be collected. *For patients who started the treatment with this drug after May 2018 (1.5-year observation period), their survival should be confirmed using the attached CRF* on the first follow-up date exceeding *1.5 years after the start of treatment at the own site.* 

The following two kinds of event will be evaluated:

- Death from any cause
- FAP-related death (Death from TTR-FAP is set as the event of interest. Death with missing cause will
  not be regarded as an event of interest.)

Time to event will be evaluated with respect to the following two kinds of time:

- Time from start of treatment to event
- Time from onset of FAP to event

CC				
I				
l				

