#### 5.4. Subgroups

Subgroup analyses for safety and efficacy will be performed with respect to the following factors:

- Patient characteristics
  - Sex [male, female]
  - Age [ $<15 \text{ yrs.}, \ge 15 \text{ to } <65 \text{ yrs.}, \ge 65 \text{ yrs.}$ ]
  - Body weight [ $\leq 50 \text{ kg}$ ,  $\geq 50 \text{ to } \leq 60 \text{ kg}$ ,  $\geq 60 \text{ kg}$ ]
  - BMI [<18.5, ≥18.5 to <25.0, ≥25]
  - Onset age [ $\leq 50$  yrs.]  $\geq 50$  yrs.]
  - Duration of disease [ $\leq 5$  yrs.]  $\geq 5$  yrs.]
  - Past treatment with this drug [present, absent]
  - Mutant genotype 2 [with V30M, without V30M]

- Karnofsky performance status [100-80, 70-50, 40-10]
- Family history of TTR-FAP [present, absent]
- Origin of patient [endemic region, non-endemic region]
- Past history of organ transplantation [present, absent]
- Past history of liver transplantation (including for purposes other than the treatment of target disease) [present (including domino liver transplantation), absent] \* Only for safety assessment
- Past history of liver transplantation other than domino liver transplantation [present, absent (including domino liver transplantation)] \* Only for efficacy assessment
- Hepatic impairment [present, absent]
- Hepatic impairment [absent, mild, moderate, severe]
- Renal impairment [present, absent]
- Baseline total NIS score [ $\leq 70$ ,  $\geq 70$ ]
- Baseline NIS-LL score [ $\leq 10$ , >10 to  $\leq 20$ , >20]
- Baseline total QOL (TQOL) score [ $\leq 20$ , >20 to  $\leq 40$ , >40]
- Severity of disease [Stage 1 (walking ability score 0-2), Stage 2 (walking ability score 3a/3b),
   Stage 3 (walking ability score 4)]

Subgroup analysis for mutant genotype will be performed only in patients with a diagnosis of mutant genotype.

- Others
  - Pretreatment (loperamide) [present, absent]
  - Pretreatment (prednisolone) [present, absent]
  - Pretreatment (rosuvastatin) [present, absent]
  - Pretreatment (NSAIDs) [present, absent]
  - Duration of treatment [ $\leq 52$  weeks, >52 to  $\leq 104$  weeks, >104 to  $\leq 156$  weeks, >156 weeks]
  - Concomitant medication (loperamide) [present, absent]
  - Concomitant medication (prednisolone) [present, absent]
  - Concomitant medication (rosuvastatin) [present, absent]
  - Concomitant medication (NSAIDs) [present, absent]

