#### 7. HANDLING OF MISSING DATA

Adverse Events

If the severity of, action taken for, or outcome of an AE is missing, their value will be considered "unknown" for data summarizations.

– NIS

If the evaluation result for the right or left side on the same day is missing, the value for the evaluated side will be adopted as the score for the item.

– QOL-DN

If the score of an item included in the Physical Function/Large Nerve Fiber Disorder subscale, Activities of Daily Living subscale, Symptoms subscale, Small Nerve Fiber Disorder subscale, or Autonomic Neuropathy subscale is missing, the missing score will be imputed with the mean score from the evaluated items in the relevant subscale as long as  $\geq 60\%$  of the items in the subscale have been evaluated. The score for the subscale will be determined by summing the scores for the evaluated and imputed items.

The TQOL score will be determined by summing the scores for the evaluated and imputed items if all the 35 items have been evaluated or all missing values imputed by using the aforementioned method. If imputation could not be done by the aforementioned method for some items because of failure of evaluation for  $\geq 60\%$  of all items in a subscale, the TQOL score will be determined as 35 times the mean from the evaluated and imputed items, provided that at least 60% of all items have been evaluated or imputed. If  $\geq 40\%$  of the items in a subscale or the TQOL score are missing, the score for the subscale and the TQOL score will be treated as missing values.

Neurological Assessment

If the item toe extension and/or toe flexion in the motor domain have been evaluated and the results are directed to normal, other items in the same domain will be imputed with those directed to normal. If the item triceps surae in the reflexes domain has been evaluated and the result is normal, other items in the same domain will be imputed with normal. If the item toe in the light touch, pin prick, vibration, or position sense domain has been evaluated and the result is normal, other items in the same domain will be imputed with normal.

- Evaluation of Survival Time

If the cause of death is missing in the record of a death-confirmed patient, the patient will be treated as having died for unknown cause.

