## PFIZER CONFIDENTIAL

- Target disease [TTR-FAP, other (TTR-FAP developing after domino liver transplantation)]
- Duration of disease (continuous)
- Duration of disease [<1 year,  $\geq$ 1 to <5 yrs.,  $\geq$ 5 to <10 yrs.,  $\geq$ 10 yrs.]
- Onset age (continuous)
- Onset age [<50 yrs.,  $\geq 50$  yrs.]
- Testing of mutant genotype [performed, not performed/unknown]
- Mutant genotype 1 [only V30M, V30M + non-V30M, only non-V30M, non-V30M + non-V30M, no mutation]
- Karnofsky performance status [100, 90, 80, 70, 60, 50, 40, 30, 20, 10]
- Karnofsky performance status [100-80, 70-50, 40-10]
- Family history of TTR-FAP [present, absent, unknown]
- Origin of patient [endemic region (Nagano Pref., Kumamoto Pref., Ishikawa Pref.), non-endemic region, unknown]
- Past history of organ transplantation [present, absent, unknown]
- Past history of liver transplantation [present (domino liver transplantation, after onset of FAP (incl. onset time unknown)), absent, unknown]
- Timing of liver transplantation (time from onset of FAP) [domino liver transplantation, ≤5 years after onset of FAP, >5 years after onset of FAP, time from onset of FAP to liver transplantation unknown]
- Hepatic impairment [absent, present (mild, moderate, severe, severity unknown), unknown]
- Renal impairment [absent, present (mild, moderate, severe, severity unknown), unknown]
- Baseline total NIS score (continuous)
- Baseline total NIS score [ $<70, \geq 70$ ]
- Baseline NIS-LL score (continuous)
- Baseline NIS-LL score [ $\leq 10$ , >10 to  $\leq 20$ , >20]
- Baseline TQOL score (continuous)
- Baseline TQOL score [ $\leq 20$ ,  $\geq 20$  to  $\leq 40$ ,  $\geq 40$ ]
- Severity of disease [Stage 1 (walking ability: 0-2), Stage 2 (3a, 3b), Stage 3 (4), undetermined]

For the following factors, summarization will be performed using the SAS:

- Disposition of non-V30M mutations [different non-V30M mutations (multiple counting allowed)]

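### SAP 6.2 defines the NIS two ways that differ by a factor of 2: the left-right mean rule caps the scores at 122/44/78, but the printed ranges are 244/88/156

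*SAP*

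**What the plan says.** SAP 6.2 describes the NIS as 37 items: cranial nerves (1-5), muscle weakness (6-24), reflexes (25-29) and sensation (30-37). The first two groups are graded 0 to 4 and the last two 0 to 2. On combining sides it says: "for items assessed bilaterally, the mean of the right and left is used as the score for the item". The score table in the same section defines each score as a sum of items and prints a range beside it: "Total score [0, 244", "NIS-LL score [0, 88" and "NIS-UL score [0, 156" (closing brackets omitted).

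SAP 7 adds that when one side is missing, "the value for the evaluated side will be adopted as the score for the item". SAP 5.4 and 8.2.2 split patients by baseline total NIS at 70 and by baseline NIS-LL at 10 and 20, without naming a scale. SAP 10.2.1 lists the 37 items but does not mark which are scored on both sides. Protocol 7.3.2.8.5 and 7.3.2.11 give the same grades and sums of items, with no left-right rule and no range.

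**The concern.** A mean of two sides cannot exceed the top grade of the item, so a sum of such means cannot reach the printed limits. Either the averaging rule or the set of ranges is wrong.

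The scale matters in three places.

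- **Reported efficacy.** SAP 8.2.4.1 summarises total NIS, NIS-LL and NIS-UL and their changes from baseline. SAP 8.2.4.7 uses NIS-LL as one of only two scores in the efficacy subgroup analyses. If means are programmed, a reader who goes by the printed 0-244 scale will see half the impairment and half the progression that the scale implies.
- **Subgroup membership.** The baseline cut-offs feed the adverse-reaction risk ratios (SAP 8.2.3.3) as well as the efficacy summaries. If scores and cut-offs are on different scales, patients fall into the wrong group.
- **Missing data.** If sums are programmed, the Section 7 rule gives an item recorded on one side only half its weight, so missing data look like less impairment.

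**Working it through.** **Inputs (SAP 6.2 and 10.2.1).** Maximum grade 4 for items 1-24 and 2 for items 25-37. NIS-LL = items 17-24, 28-29 and 34-37. NIS-UL = items 1-5, 6-16, 25-27 and 30-33.

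**Step 1: reproduce the printed ranges.** Add right and left for every item:

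- Total: 2 × (24×4 + 13×2) = 2 × 122 = 244
- NIS-LL: 2 × (8×4 + 2×2 + 4×2) = 2 × 44 = 88
- NIS-UL: 2 × (5×4 + 11×4 + 3×2 + 4×2) = 2 × 78 = 156

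All three match.

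**Step 2: apply the rule as written.** Under a mean, a bilateral item contributes at most 4 or 2, and so does an item with a single score. The result does not depend on which items are bilateral: 122, 44 and 78.

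**Step 3: try partial sums.** Items such as Respiratory (6) and Neck Flexion (7) might carry a single score.

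| Rule | Total | NIS-LL | NIS-UL |
|---|---|---|---|
| Mean of sides | 122 | 44 | 78 |
| Sum, items 1-7 single | 216 | 88 | 128 |
| Sum, items 6-7 single | 236 | 88 | 148 |
| Sum, item 6 single | 240 | 88 | 152 |
| Sum, all 37 items on both sides | 244 | 88 | 156 |
| Printed | 244 | 88 | 156 |

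Each item can contribute at most twice its top grade, so 244 is reached only if every item is doubled.

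**Step 4: compare the other bilateral scale.** For the neurological assessment, SAP 6.2 says "Each evaluation item will be evaluated bilaterally except those for the trunk". Summing both sides and counting the trunk once gives:

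- Motor: 16×5×2 = 160
- Reflexes: 5×1×2 = 10
- Sensation: 2×(10×2×2 + 2) + 6×2×2 + 4×2×2 = 124
- Total: 160 + 10 + 124 = 294

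These equal the printed ranges. Averaging would give 80, 5, 64 and 149. The ranges on that scale are therefore true maxima of two-sided sums.

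**Step 5: cut-offs as a share of the maximum.**

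- Total 70: 70/122 = 57%, or 70/244 = 29%
- NIS-LL 10: 10/44 = 23%, or 10/88 = 11%
- NIS-LL 20: 20/44 = 45%, or 20/88 = 23%

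**Step 6: who would move if the scales differ.**

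- *Cut-offs set on the summed scale, means programmed:* summed totals from 70 to below 140 drop into the below-70 group. Summed NIS-LL above 10 to 20 drops to the lowest group, and above 20 to 40 to the middle group.
- *Cut-offs set on the mean scale, sums programmed:* mean totals from 35 to below 70 rise into the 70-and-over group. Mean NIS-LL above 5 to 10 rises to the middle group, and above 10 to 20 to the top group.
- *Scores and cut-offs on one scale:* nobody moves.

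**Step 7: a missing side under a sum.** An item graded 4 on the recorded side scores 4, where 4 on both sides would give 8. If one whole side is missing, the NIS-LL maximum is 44 instead of 88.

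**The case against.** The strongest reply is that the two readings do not have equal support. The only instruction on combining sides is the mean, Section 7 follows the same logic, and no sentence tells anyone to add right and left for NIS. A programmer following the text would compute means. The bracketed ranges would then be mislabelled annotations, and the half-weight problem would not arise. The neurological assessment is not proof either: it has no mean rule, and two scales may be scored differently on purpose. Subgroup movement is conditional, nothing shows that the cut-offs were set on a different scale from the scores, and a consistent factor of 2 leaves direction and relative change intact.

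Much of this is fair. The text leans towards a mean, and the half-weight effect needs a departure from the written rule. The case report form, which is not among the documents, may show which items have two sides. The contradiction remains, however. Three ranges are each exactly double what the rule allows, which points to a scale built on two-sided sums rather than to a stray digit. Absolute NIS values and changes are what the plan reports, and those do change by a factor of 2.

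**Conclusion.** The concern holds. SAP 6.2 gives two incompatible definitions of the NIS scores, a factor of 2 apart: 122 against 244, 44 against 88, and 78 against 156. The arithmetic rests only on the item lists and grades in the SAP. The documents do not show which statement is the slip.

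The consequence is bounded. NIS is one of 10 effectiveness items in Protocol 7.3.2.11, none is designated primary, and SAP 4.1 and 4.2 specify no hypotheses or decision rules. No test is invalidated. But these descriptive values are the NIS efficacy result, and under SAP 3 the final analysis supports the reexamination application, so the scale has to be fixed. Any subgroup effect depends on scores and cut-offs being on different scales. Its size cannot be computed without a baseline NIS distribution.

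**What to change.** Adopt one rule and align everything to it.

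- **Option A, sum.** State that right and left are added and that all 37 items, including 6 and 7, count on both sides. Keep the ranges 0-244, 0-88 and 0-156. Change Section 7 so that the recorded side is doubled when the other is missing. If the case report form shows that some items have a single score, the ranges for total and NIS-UL must come down accordingly (for example to 236 and 148 if items 6-7 are single).
- **Option B, mean.** Keep the mean rule and Section 7, and correct the ranges to 0-122, 0-44 and 0-78. A list of bilateral items is not strictly needed here, because the maxima do not depend on it.

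Under either option, state in 5.4 and 8.2.2 which scale the cut-offs 70, 10 and 20 belong to, and rescale them only if they were set on the other one. Check that the derivation code follows the chosen rule.

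The cost is a few lines in SAP 5.4, 6.2, 7 and 8.2.2 and one code check. No new data are needed.

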7.3.2.8. Tests/clinical laboratory tests

For the following test items conducted from the first day of treatment with this drug until the end of the observation period (or date of discontinuation of treatment with this drug), enter the test dates (dates of measurement) and test results. For the tests conducted before the start of treatment with this drug, enter the test results immediately before the first day of treatment (including the first day of treatment). For clinically significant fluctuations compared to those before the start of treatment with this drug, enter the details in the adverse event column.

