7.3.2.8.1. Clinical laboratory tests

(1) Hematology: White blood cell count, neutrophil count, lymphocyte count, red blood cell count, platelet count, hemoglobin, prothrombin time

(2) Biochemistry: AST (GOT), ALT (GPT), AL-P, LDH, γ -GTP, total bilirubin, triglycerides, serum creatinine, serum albumin

(3) Endocrine test: Thyroid-stimulating hormone (TSH), total T4, free thyroxine (FT4)

(4) Urinalysis: Urine protein (qualitative)

Pfizer Confidential Page 17 of 37

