7.3.2.8.2. General tests

- (1) Height
- (2) Weight
- (3) Pulse
- (4) Blood pressure (systolic/diastolic)

7.3.2.8.3. Plasma concentration of tafamidis (to be performed only for patients with severe hepatic impairment)

If the patient has severe hepatic impairment, measure the plasma concentration of tafamidis as much as possible and enter the following information. If the patient has hepatic function disorder at the start of treatment with this product, enter the details in the section of "Presence or absence of hepatic/renal impairment" and if it occurred during the observation period, enter the details in the section of "Adverse Events". If a laboratory test related to hepatic impairment is performed, enter the test results in the section of "Laboratory tests" or the section of "Tests for adverse events".

For the detailed method of measuring plasma concentration of tafamidis, refer to the Appendix to Guidelines for Special Investigation "Procedures for Measurement Plasma Concentration of Tafamidis in Patients with Severe Hepatic Impairment" (Appendix 1).

- (1) Record of medicines immediately before blood sampling (date and time of medicines)
- (2) Record of blood sampling (date and time of blood sampling)
- (3) Plasma concentration of tafamidis

Table 3. Child-Pugh Classification

*Overseas clinical studies were conducted by defining moderate hepatic impairment as Child-Pugh score of ≤ 9 . [Reference: Child-Pugh classification] The scores for each item are totaled and 5 to 6 points are classified as A, 7 to 9 points as B, and 10 to 15 points as C.

[Child-Pugh classification]	1 point	2 points	3 points
Hepatic encephalopathy	None	Mild	Occasional coma
Ascites	None	Small amount	Moderate amount
Total serum bilirubin (mg/dL)	<2.0	2.0-3.0	3.0<
Serum albumin (g/dL)	3.5<	2.8-3.5	<2.8
Prothrombin time (%)	70<	40-70	<40

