7.3.2.11. Effectiveness evaluation

The following 10 items should be evaluated for effectiveness:

(1) NIS (See Section 7.3.2.8.5.)

Evaluate the NIS total score, the NIS Upper Limb (NIS-UL) total score, the NIS Lower Limb (NIS-LL) total score, scores of cranial nervous system (sum of items 1 to 5), muscle weakness (sum of items 6 to 24), tendon reflex (sum of items 25 to 29), and sensation (index finger: sum of items 30 to 33, great toe: sum of items 34 to 37).

(2) Norfolk QOL-DN (See Section 7.3.2.8.6.)

Evaluate the TQOL scores (sum of all 35 items) and 5 domain scores (physical function/large nerve fiber disorder score, activities of daily living score, symptom score, small nerve fiber disorder score, and autonomic neuropathy score).

(3) Modified Body Mass Index (mBMI)

mBMI is calculated by multiplying BMI by serum albumin level.

(4) Ambulatory status (ambulatory ability scale in polyneuropathy dysfunction score)

Evaluate the ambulatory status (see Section 7.3.2.8.7 for details).

(5) Motor

Evaluate the motor function with MRC (16 items in total) (see Section 7.3.2.8.8 for details) scale. (6) Reflexes

Evaluate the tendon reflexes (5 items in total) (see Section 7.3.2.8.8 for details).

(7) Light Touch

Evaluate the tactile (11 items in total) (see Section 7.3.2.8.8 for details).

(8) Pin Prick

Evaluate the pain sensation (11 items in total) (see Section 7.3.2.8.8 for details). (9) Vibration

Evaluate the vibration sense (6 items in total) (see Section 7.3.2.8.8 for details). (10) Position Sense

Evaluate the positional sense (4 items in total) (see Section 7.3.2.8.8 for details).

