7.3.2.12. Adverse events

Occurrence of adverse events (AEs) from the start date of administration of this drug to the end date of observation period should be confirmed and the following information should be recorded. If any AE is

observed, the investigator will take appropriate measures, promptly report it to Pfizer, and in principle, transcribe and confirm the course until the symptom disappears.

Also, further investigation should be separately conducted, if deemed necessary by Sponsor for patients who experienced a serious adverse reaction, an unexpected adverse reaction or other adverse reactions not listed in the package insert.

- (1) Presence/absence of AE
- (2) Name of AE
- (3) Date of occurrence
- (4) Intervention
- (5) Seriousness
- (6) Outcome
- (7) Causal relationship to this drug

If the AE is associated with abnormal laboratory values, i.e., clinical laboratory tests, the following information should also be recorded:

- (1) Laboratory parameter
- (2) Site reference value
- (3) Unit
- (4) Date measured
- (5) Results

Note: AEs are any and all unfavorable events (including clinically significant abnormal changes in laboratory tests) occurring in patients after starting the targeted drug treatment regardless of their causal relationship. Serious adverse events (SAEs) are any unfavorable medical occurrences that result in death, are life-threatening, require (or prolong) hospitalization, cause persistent or significant disability/incapacity, result in congenital anomalies or birth defects, or are other conditions which represent significant health hazards.

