7.7. Data analysis

1. Definition of analysis set

The safety analysis set (SAS) consists of all patients who received this drug at least once. The effectiveness analysis set consists of those for whom the effectiveness evaluation was conducted at least once among the SAS. The details will be described in the separately prescribed Statistical Analysis Plan (SAP).

2. Method of analysis

(1) Major analysis for safety evaluation

The occurrence of ADRs and the incidence of ADRs (percentage of patients with AEs for which the causal relationship with this drug cannot be ruled out) will be calculated in the SAS.

(2) Major analysis for effectiveness evaluation

For NIS, QOL-DN, and mBMI, their values and changes from baseline at each time point will be calculated in the effectiveness evaluation set. For ambulatory status, motor function (MRC), tendon reflex, tactile sense, pain sensation, vibration sense, and positional sense, changes from baseline at each time point will be calculated. In addition, survival time analysis will be performed using survival information obtained up to 3 years after the start of treatment.

Detailed methodology for summary and statistical analyses of data collected in this study will be documented in a SAP, which will be dated, filed and maintained by Pfizer. The SAP may modify the plans outlined in the protocol; any major modifications of primary endpoint definitions or their analyses would be reflected in a protocol amendment.

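### SAP 6.2 divides albumin labelled g/dL by 10 in the mBMI formula, which gives one tenth of the protocol's product if the data are in g/dL

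*SAP*

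**What the plan says.** SAP 6.2 (Efficacy Endpoints) gives the derivation. It begins "mBMI = (serum albumin", continues with the unit label g/dL and a division by 10, and multiplies the result by BMI. The next line defines BMI with height written as "body height [cm]/100)^2".

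Protocol 7.3.2.11 (3) states: "mBMI is calculated by multiplying BMI by serum albumin level". It gives no divisor and no unit.

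On the albumin measurement itself:
- Protocol 7.3.2.8.1 lists it without a unit among the biochemistry items: "total bilirubin, triglycerides, serum creatinine, serum albumin".
- Protocol 7.3.2.8 tells sites to "enter the test dates (dates of measurement) and test results".
- Protocol 7.3.2.12 names unit as a field to record only under the condition "If the AE is associated with abnormal laboratory values".
- Apart from the SAP formula, the only albumin unit is in the Child-Pugh reference table (Protocol Table 3), whose row begins "Serum albumin (g/dL". That table does not concern mBMI.

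On use, Protocol 7.7 says: "For NIS, QOL-DN, and mBMI, their values and changes from baseline at each time point will be calculated". SAP 8.2.4.3 summarises mBMI values and changes from baseline, and SAP 9 lists mBMI among the efficacy endpoints.

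**The concern.** In the BMI line the SAP writes an input unit followed by a divisor, and the divisor is a valid conversion: centimetres over 100 gives metres. Read the same way, the albumin term is not a valid conversion. Since 1 g/dL = 10 g/L, dividing by 10 takes g/L to g/dL. A value already in g/dL, divided by 10, lands on a scale that appears nowhere else in the documents and is one tenth of what the protocol's definition gives in g/dL.

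What is at stake is the scale of a named effectiveness measure. Neither document gives an mBMI unit, expected range or reference value, so a reader of the tables would have nothing against which to notice a tenfold shift. Absolute means and changes could not safely be set beside mBMI figures from elsewhere.

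**Working it through.** The documents give no mBMI value, so there is no figure of the plan's own to reproduce. The check is a comparison of two definitions.

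**Inputs**
- Conversion: 1 g/dL = 10 g/L.
- Illustrative albumin: 3.5 and 2.8 g/dL, the cut-offs in Protocol Table 3.
- Illustrative BMI: 18.5 and 25.0, the category limits in SAP 5.4.

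These values are borrowed as convenient points. They are not patient data.

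**General form.** Let A be albumin in g/dL and B be BMI.
- Protocol product in g/dL: A × B.
- SAP formula applied literally to g/dL data: (A/10) × B = (A × B)/10.
- Ratio of SAP to protocol: 1/10 for every A and B.

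**Single values**

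| Albumin (g/dL) | BMI | SAP formula, g/dL data | Protocol product, g/dL |
|---|---|---|---|
| 3.5 | 18.5 | (3.5/10) × 18.5 = 6.475 | 3.5 × 18.5 = 64.75 |
| 2.8 | 18.5 | (2.8/10) × 18.5 = 5.18 | 2.8 × 18.5 = 51.8 |
| 3.5 | 25.0 | (3.5/10) × 25.0 = 8.75 | 3.5 × 25.0 = 87.5 |

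**Change from baseline**, albumin falling from 3.5 to 2.8 g/dL at BMI 18.5:
- SAP formula: 5.18 − 6.475 = −1.295, and −1.295/6.475 = −20%.
- Protocol product: 51.8 − 64.75 = −12.95, and −12.95/64.75 = −20%.

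The absolute change differs tenfold; the percent change and the direction agree.

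**If the database holds g/L.** The same patient has albumin 35 g/L. The printed operation then gives (35/10) × 18.5 = 64.75, equal to the protocol product in g/dL. In that case the division is right and only the label is wrong.

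**Reach of the effect.** A constant multiplier carries through to means, SDs, medians, minima, maxima and absolute changes at every mBMI time point in SAP 6.2, and to the listing in SAP 9. It touches no inference: SAP 4.1 and 4.2 state that hypotheses and decision rules do not apply, and the efficacy subgroups in SAP 8.2.4.7 use NIS-LL and TQOL, not mBMI.

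**The case against.** The strongest reply is that the SAP formula is complete as printed: one input unit, one operation, one result. A programmer who follows it obtains one scale. Protocol 7.7 leaves detailed methods to the SAP and allows it to modify the protocol's plans, so a divisor is not an error merely because the protocol lacks one. Reading the divisor as a failed conversion rests on analogy with the BMI line, and a deliberate scaling constant cannot be strictly excluded. The formula was also read by machine from a PDF.

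Much of this stands. It is why the point concerns a mismatch as printed and why checking the page comes first. It does not remove the mismatch: the operation beside the label is the one that would be needed for a different label, and nothing readable offers another reason for it.

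A reader might infer more than the documents support:
- *The scale of mBMI is undefined, or two programmers would get different answers.* They would differ only if one ignored part of the formula.
- *The values are off by a factor of 100.* That requires an mBMI product in g/L, which no passage mentions. g/dL is the only albumin unit in either document.
- *The albumin unit was never specified to sites.* The case report form is not among the documents and may print it.
- *Reported results are wrong.* If albumin is stored in g/L, the numbers are those of the protocol's product in g/dL.
- *The protocol must be amended.* Protocol 7.7 requires an amendment only for major changes to primary endpoint definitions or their analyses; a SAP clarification is enough.

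**Conclusion.** The point holds as a minor error in a stated derivation rule. The division by 10 in SAP 6.2 does not fit its own g/dL label. Taken literally on g/dL data, it yields one tenth of the protocol's definition, a constant factor of 10 on the mBMI summaries, absolute changes and listings.

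This size rests on two assumptions: that albumin is held in g/dL, the only unit the documents show, and that all values share that unit. If units were mixed across sites, the distortion would not be one constant. If all values are in g/L, the numbers stand and only the label needs correcting.

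Confidence is high that label and operation disagree in the text as read, and medium that any reported number is affected. Parts of the SAP are redacted, so the absence of an explanation refers to readable text only.

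**What to change.** All changes are in the SAP, its outputs and the program:

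1. Confirm the formula on the original SAP page, and confirm the unit in which albumin is stored, including that it is the same for all records.
2. Make label and operation agree:
   - data in g/dL: remove the division by 10, or replace it with multiplication by 10 if a product in g/L is intended;
   - data in g/L and a product in g/dL intended: keep the division and change the label to g/L.
3. State the mBMI unit in SAP 6.2 and in the headers of the mBMI tables and listing.
4. Check the derivation program against the corrected formula.

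The cost is one label or operator, one unit in the text and headers, and one line of code to verify. No new data are needed. If all albumin values share one unit, any mBMI values already derived can be rescaled exactly by a constant.
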